We will test the feasibility of a “combined chronotherapy” (CC) intervention consisting of morning BLT and evening BLB, administered daily for 4 weeks in patients who experienced ACS. This will be a two-phase pilot study. Phase A of the study will be a single-arm open-label study of the home-based CC intervention in 5 post-ACS patients. Phase B of the study will be a parallel-arm randomized clinical trial (RCT) in which 15 post-ACS patients will be randomized (using a 2:1 allocation) to active CC treatment or sleep hygiene education control group. In Phase A, we are primarily concerned with study feasibility, acceptability, appropriateness, and usability. In Phase B, we will additionally assess whether the intervention engages its proposed proximal target mechanism – sleep. Consenting participants who indicate habitual sleep that is of short duration and/or poor quality after ACS will be eligible for inclusion.

Primary Aim: Determine the feasibility of administering the CC intervention in this population.

We will assess a) feasibility, b) acceptability, c) appropriateness, d) usability, and e) adherence of the 4-week CC intervention in ACS survivors with poor sleep.

Primary Aim will be tested by assessing the following measures:

- (1) proportion of participants who complete the outcome assessments at study conclusion;
- (2) proportion of participants who report scores ≥ 4 for their final rating of the intervention’s feasibility;
- (3) proportion of participants who report scores ≥ 4 for their final rating of the intervention’s acceptability;

- (4) proportion of participants who report scores ≥ 4 for their final rating of the intervention's appropriateness for improving sleep;
- (5) proportion of participants who report total scores ≥ 68 for their final rating of the intervention's usability.
- (6) proportion of who report administering the intervention (i.e., morning BLT and evening BLB) on $\geq 50\%$ (and $\geq 75\%$) of the days throughout the 4-wk treatment period.

Secondary Aim 1: Determine whether the CC intervention engages its target mechanism: sleep.

We will assess insomnia, sleep quality, and sleep duration at baseline and at the end of the 4-week intervention period, and will evaluate whether the CC intervention leads to greater changes in sleep-related outcomes relative to the control condition.

Secondary Aim 1 will be tested by assessing the following measures:

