- (1) Baseline-to-study conclusion change in insomnia severity (measured as the within-person difference in the total score of Insomnia Severity Index);
- (2) Baseline-to-study conclusion change in global sleep quality severity (measured as the within-person difference in the total score of Pittsburgh Sleep Quality Index [PSQI]);
- (3) Baseline-to-study conclusion change in sleep duration (measured as the within-person difference in the sleep duration subscale of the PSQI and actigraphy);

2. Study Design

To achieve these aims, we propose to enroll a total of 20 patients who have experienced an ACS event into this two-phase study. Phase A will be a single-arm open-label study of the home-based CC intervention in 5 post-ACS patients. Phase A will consist of English-speaking patients only. Phase A will primarily assess feasibility of enrollment and administering the intervention. After all 5 Phase A participants enroll and complete the study procedures, we will implement Phase B of the study. Phase B is an RCT in which 15 post-ACS patients will be enrolled and randomized (using a 2:1 allocation) to active CC treatment or sleep hygiene education control group. Phase B will consist of both English and Spanish-speaking patients. Participants cannot enroll in both Phase A and Phase B of this protocol.

Overview of Phase A Study Design:

Screening and consent:

Our recruitment strategy is multi-faceted and will include recruiting NYP patients who experienced an acute coronary syndrome (ACS) event within the past 3 months.

The study team will first confirm eligibility and obtain approval from the treating clinician as described in the Recruitment and Enrollment section to contact the patient and discuss the study. Patients who are interested and verbally consent to the study will undergo a pre-screening questionnaire to determine eligibility. All study procedures can occur in-person, over the phone, or online via Zoom (a web-based, HIPAA-compliant video-conferencing platform associated with Columbia University Irving Medical Center). Participants will complete a screening questionnaire to collect demographics, contact information, and participant sleep quality and habits. Additional eligibility will be determined during the screening questionnaire. Phase A participants will view two educational videos (~5 minutes each in length) that will provide information about the basics of sleep, the regulation of sleep (including aspects

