The study team will first confirm eligibility and obtain approval from the treating clinician as described in the Recruitment and Enrollment section to contact the patient and discuss the study. Patients who are interested and verbally consent to the study will undergo a pre-screening questionnaire to determine eligibility. All study procedures can occur in-person, over the phone, or online via Zoom (a web-based, HIPAA-compliant video-conferencing platform associated with Columbia University Irving Medical Center). Participants will complete a screening questionnaire to collect demographics, contact information, and participant sleep quality and habits. Additional eligibility will be determined during the screening questionnaire. After completing the screening questionnaire, Phase B participants will be randomized to either the CC intervention arm or sleep hygiene education control group (in a 2:1 ratio). All participants will view two educational videos (~5 minutes each in length) that will provide information about the basics of sleep, the regulation of sleep (including aspects of how the external light environment impacts sleep), the relationship of sleep with health, function, and well-being and tips for achieving good sleep. Participants will have the option of watching the educational videos during hospitalization or at home for those with internet access and participants will also be given a written summary of the contents of the educational videos.

Phase B participants randomized to the active CC arm will then be instructed on how to administer the CC intervention. The CC intervention will consist of a wearable light visor to administer the BLT each morning for 30 minutes after awakening, and the BLB glasses to be worn each night from 8:00pm to bedtime. Instructions on how to use the intervention devices will be offered in person during enrollment, over the phone, or online via Zoom after the participant has returned home.

Visit 1/Baseline: After verbally agreeing to participate and enroll in the study, Phase B participants will be scheduled for Visit 1 (either in person, telephone, or video on Zoom). During Visit 1, participants will complete a questionnaire battery on their sleep, PTSD symptoms, and cardiac anxiety. Participants who were unable to view the education videos during enrollment will be able to do so during Visit 1.

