Secondary Aim 1: Determine whether the CC intervention engages its target mechanism: sleep. *We will assess insomnia, sleep quality, and sleep duration at baseline and at the end of the 4-week intervention period, and will evaluate whether the CC intervention leads to greater changes in sleep-related outcomes relative to the control condition.*

Secondary Aim 1 will be tested by assessing the following measures:

- (1) Baseline-to-study conclusion change in insomnia severity (measured as the within-person difference in the total score of Insomnia Severity Index);
- (2) Baseline-to-study conclusion change in global sleep quality severity (measured as the within-person difference in the total score of Pittsburgh Sleep Quality Index [PSQI]);
- (3) Baseline-to-study conclusion change in sleep duration (measured as the within-person difference in the sleep duration subscale of the PSQI);

Statistical approach for Secondary Aim 1. We will test this aim by evaluating the change scores in measures listed above. We hypothesize that the pattern of means will reveal a reduction in insomnia symptom severity, an improvement in global sleep quality, and an increase in self-reported sleep duration in the CC intervention group. As mentioned above, this Phase-I trial is not powered to test the significance of these sleep-related changes.

General Approach. For descriptive statistics, categorical data will be presented as percentages and continuous data will be presented as means with standard deviations for normally distributed measures and as median with interquartile range for measures that are not normally distributed. Checks of assumptions (e.g., normality) underlying statistical procedures will be performed and corrective procedures will be applied (e.g., log transformation or nonparametric tests).

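### Secondary Aim 1 asks about CC relative to control, but the SAP names no between-arm estimate and its only sleep hypothesis concerns the CC group

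*SAP*

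**What the plan says.** The SAP's Secondary Aim 1 states that the study "will evaluate whether the CC intervention leads to greater changes in sleep-related outcomes relative to the control condition". The protocol carries the same aim and ties it to the randomised phase: "In Phase B, we will additionally assess whether the intervention engages its proposed proximal target mechanism", namely sleep.

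The three SAP measures (Insomnia Severity Index total, PSQI total, PSQI sleep duration) are each defined as a within-person difference from baseline to study conclusion. Under Statistical approach for Secondary Aim 1 the method is: "We will test this aim by evaluating the change scores in measures listed above". The hypothesis that follows predicts less severe insomnia symptoms, "an improvement in global sleep quality, and an increase in self-reported sleep duration in the CC intervention group". Control is not mentioned. The SAP then says that "this Phase-I trial is not powered to test the significance of these sleep-related changes".

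The General Approach offers means with SDs or medians with interquartile ranges. If assumption checks fail, "corrective procedures will be applied (e.g., log transformation or nonparametric tests"). It does not mention a between-arm difference or a confidence interval, and the protocol has no statistical section that supplies one.

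**The concern.** The aim is comparative and the stated hypothesis is not. A mean improvement among CC patients satisfies the hypothesis whether or not control patients improved just as much. Sleep could improve in both arms through recovery, since enrolment is within 3 months of the coronary event, or through the education videos that Phase B shows to everyone. A report could therefore describe the hypothesis as supported without having answered whether CC does better than control.

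It is also unclear whether the SAP's CC group includes the five Phase A patients, who received CC with no concurrent control. Adding them would enlarge the CC mean's sample without adding anything to the randomised comparison.

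**Working it through.** **Inputs from the documents.** Phase B randomises 15 patients 2:1, so 15 × 2/3 = 10 CC and 15 × 1/3 = 5 control. Phase A adds 5 on CC alone, for a total of 20. Both Phase B arms complete the baseline questionnaires at Visit 1 and repeat them at Visit 2, four weeks later, so a contrast can be computed. The documents give no SD, effect size, alpha or power figure for this aim, so there is no stated figure to reproduce.

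**Step 1: what a CC-only reading can show.** Assume that CC has no effect, both arms improve by d (in SDs of the outcome), and the baseline-to-follow-up correlation is r = 0.5 to 0.7. The SD of change is then √(2(1−r)) outcome SDs. Under normality, the chance that the mean of 10 CC patients moves in the predicted direction on one outcome is Φ(d√10 / √(2(1−r))). For example, d = 0.2 and r = 0.5 give Φ(0.632/1) = 0.736.

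| Assumed shared improvement d | CC mean, r = 0.5 | CC mean, r = 0.7 | CC minus control |
|---|---|---|---|
| 0 | 0.500 | 0.500 | 0.500 |
| 0.1 | 0.624 | 0.658 | 0.500 |
| 0.2 | 0.736 | 0.793 | 0.500 |
| 0.3 | 0.829 | 0.890 | 0.500 |
| 0.5 | 0.943 | 0.979 | 0.500 |

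The contrast is unaffected by d. At d = 0 the two readings do not differ.

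**Step 2: precision of the contrast.** The unadjusted 95% half-width, in SDs of change, is t × √(1/n₁ + 1/n₂).
- 10 versus 5: 2.160 × √(1/10 + 1/5) = 2.160 × 0.548 = 1.18.
- 9 versus 4: 2.201 × √(1/9 + 1/4) = 2.201 × 0.601 = 1.32.

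For illustration, an assumed SD of change in the Insomnia Severity Index of 4 to 7 points gives ±4.7 to ±8.3 points. At two-sided 5% (also an assumption), power at 10 versus 5 is 14% for a difference of 0.5 SD of change, and 80% power needs about 1.66 SD. This supports an estimate with an interval in place of a test.

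**Step 3: adjusted or change score.** In 40,000 simulated trials at 10 versus 5, the mean 95% half-width in outcome SDs was:

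| r | Difference in mean change | Baseline-adjusted |
|---|---|---|
| 0.5 | 1.159 | 1.055 |
| 0.6 | 1.038 | 0.974 |
| 0.7 | 0.897 | 0.869 |

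Coverage was 0.948 to 0.952. Adjustment gains a little in each case. The 1.159 sits just below 1.183 because it averages over sample SDs, which are slightly small on average.

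**Step 4: what the contrast does not remove.** The protocol's Phase B overview says: "After completing the screening questionnaire, Phase B participants will be randomized to either the CC intervention arm or sleep hygiene education control group". Visit 1 comes later and is self-reported, and no blinding is described. If knowing the allocation shifted CC baseline reports by an assumed 0.2 SD, the error would be 0.20 SD for the change-score contrast and r × 0.2 = 0.10 to 0.14 SD for the adjusted one. A shift in Visit 2 reporting would enter both in full.

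**The case against.** The strongest reply is that the comparison is already planned. The aim names the control condition, the approach says it tests this aim, and with two arms and change scores a difference in change is the natural reading. That stands as to intent. A reader might infer from the hypothesis that the SAP means to ignore the control arm, and the documents do not support that. But intent does not fix an estimator, and the one prediction against which results can be judged leaves control out.

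A second reply is that the probabilities score a rule the SAP does not contain. This is also fair. The SAP sets no success criterion based on the sign of the means, on one outcome or on all three together, so the figures in Step 1 are not an error rate of this plan. They show only how little a CC-only improvement says about CC against control.

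A third is that shared improvement is speculative. It is assumed here. Selection uses screening questions, whereas the Insomnia Severity Index and PSQI are first taken at Visit 1, so regression to the mean after baseline need not be large. Many participants may also see the videos before Visit 1. To conclude that shared improvement will occur, or will mislead, would go beyond the documents.

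Finally, the pilot is small and disclaims power. That excuses the absence of a significance test. It does not explain leaving the comparative estimate unnamed.

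**Conclusion.** The concern holds in a limited form. The approach and hypothesis for Secondary Aim 1 do not match the comparative question, and neither document names a between-arm estimate or interval. The aim's wording shows that a comparison is intended; what is missing is its specification.

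The size depends on a shared improvement that the documents do not give. Over an assumed 0 to 0.5 SD, with correlation 0.5 to 0.7 and no CC effect, a single CC mean moves in the predicted direction with probability 0.50 to 0.98, while the contrast stays at 0.50. The point should be fixed, but the stakes are modest: this is a secondary aim of a pilot whose primary aim is feasibility.

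The protocol's duration measure is the "sleep duration subscale of the PSQI and actigraphy", whereas the SAP's omits actigraphy. That is a separate discrepancy and adds no weight here.

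**What to change.** Before the Phase B sleep data are analysed, add to the Secondary Aim 1 approach:

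> In randomised Phase B participants only, we will estimate the CC-minus-control difference at Visit 2 in ISI total, PSQI global score and PSQI sleep duration, adjusted for the Visit 1 value, with a 95% CI. This is estimation, and no significance claim will be made.

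- Name this as the single estimator, and state that the General Approach's switch after assumption checks does not apply to it. Such checks are weak at this size: in simulation, a Shapiro-Wilk test rejected exponential data 16% of the time at n = 5 and 45% at n = 10. A rank-based fallback would change what is estimated, and its exact level does not carry over to tied questionnaire scores.
- The unadjusted difference in mean change may be shown as a supporting result, which keeps the link to the SAP's change scores.
- Reword the hypothesis as CC relative to control.
- Report the five Phase A participants separately and descriptively.
- State as a limitation that Visit 1 is self-reported after randomisation, so the contrast removes shared change but not expectancy or reporting differences.

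The cost is a few sentences and three small analyses of questionnaires that both arms already complete. The downside is a visibly wide interval, about ±1.18 SD of change unadjusted at 10 versus 5 and ±1.32 at 9 versus 4, which is consistent with the SAP's statement that the trial is not powered for these outcomes.
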